8.2 Platform Trial Cohort (PTC)

All participants who meet CTU eligibility criteria (see sections [7.1](#) and [7.2](#)) will be enrolled in the PTC and will participate in the BHSP study with monitoring of their engagement over the course of 12-months. Data collected during the BHSP study will be used to model the Open Platform Trial (OPT) to conduct future RCTs utilizing participants from the PTC (Phase B of CTU). Once participation in the BHSP study has ended, participants may be offered potential participation in future multidomain intervention RCTs of the CTU program under separate protocols. For participants who are interested and meet inclusion criteria for specific RCTs within the OPT, a separate informed consent will be signed prior to participation.

8.3 Brain Health Pro (BHPro) Intervention

The BHPro Intervention is a 45-week, multidomain, web-based formal educational program designed to increase dementia literacy, foster engagement, and convey best available evidence for lifestyle changes that can mitigate dementia risk. The program was developed as a collaborative effort by CCNA investigators with recognized expertise in the program's content areas, along with input from older-adult citizen advisors. The program was refined and updated based on feedback from focus-groups and a 3-month pilot study to assess usability and accessibility.

Participants will receive instructions on how to register and participate in the program at the remote baseline study visit.

8.3.1 *Program Content*

Participants will register on the BHPro website and obtain a personal password. Participants will need to provide a valid e-mail address and password in order to login and participate in BHPro. Participants will also be asked to enter a preferred name (this can be a first name or nickname), which they will be referred to as throughout their participation in the program. Name and e-mail address will not be included in the study data set. All data from BHPro will be de-identified and linked to the LORIS PSCID prior to being included in the CTU database. Registration will also include viewing a brief video explaining the program, demographic questions and lifestyle questionnaires including general questions related to socio-demographic profile, health, and lifestyle.

BHPro is organized into the following 8 content modules:

1	Motivation, self-efficacy, positive health, dementia, environment vs genetic risk, cognitive aging and healthy lifestyle, medication
2	Physical activity
3	Cognitive engagement
4	Diet
5	Sleep
6	Social and Psychological Health
7	Vascular health
8	Vision and hearing

The program content is provided progressively to deliver new weekly content (i.e. module chapters) of approximately 40 minutes. Participants will have access to new content on 4 modules each week (10 minutes/module; alternating every 2 weeks) through an email push notification, as an approach to maintain interest. Participants will be invited to visit the web site at their own rate but encouraged to spend a minimum of 40 minutes/week on the program.

Information is organized as chapters within the modules, which contain scientific evidence, explanation of principles and mechanisms that underlie positive effects, specific recommendations (e.g., type and dose of prescribed physical exercises), suggestions to improve behavior in everyday life and typical barriers and tips to circumvent them. Content format will include visual and auditory text, pictures, animations, quizzes, questionnaires and interactive exercises.

8.3.2 **Personalized Profiles on Modifiable Lifestyle Risk Factors**

Participants will be asked to complete brief online lifestyle risk questionnaires approximately every 3 months (see [Appendix 3](#) for descriptions of the BHPro Lifestyle Risk Questionnaires). Questions will be related to the content in the program modules (e.g. sleep, diet, physical activity, cognitive engagement, social and psychological health, sensory). A personalized profile will be developed for each participant based on their responses to the lifestyle questionnaires. Participants will also be asked to set goals based on their risk profile and to re-visit and update their goals every three months. Participants will be encouraged to focus on the content modules that are related to their risk profile. Although participants will have access to all content modules within the program, modules that are suggested to the participant based on their risk profile will be highlighted.

8.3.3 **BHPro Outcome Variables and Data Collection**

The following data and assessments will be collected directly through BHPro. For more detailed information on the specific instruments see section [10.0](#). (Study Specific Instruments):

Outcome	Measure/Data Collected	Frequency
Engagement using BHPro	Direct monitoring of several parameters that could include: - Dates and time of program use - % completion of chapters at regular intervals - % completion of questionnaires - Other parameters may be added to this list as the studies goes on	Weekly/monthly
Acceptability (usefulness and ease of use) of BHPro	Adapted version of the Technology Acceptance Model questionnaire	Every 6 months
Usability of the BHPro	Adapted web-based version of the System Usability Scale (SUS)	Every 6 months
Dementia Literacy	Alzheimer Disease Knowledge Scale (ADKS)	Every 6 months
Participant Self-Efficacy	General Self-Efficacy Scale (GSE)	Every 6 months

Outcome	Measure/Data Collected	Frequency
Attitudes towards dementia and dementia screening	Sections B and D from The Perceptions Regarding Investigational Screening for Memory in Primary Care (PRISM-PC) Questionnaire	Every 6 months

9.0 STUDY PROCEDURE DESCRIPTIONS

9.1.1 ***Sociodemographics***

Sociodemographic data (sex, gender identity, age, handedness, languages, marital/partner status, living circumstances, reproductive history, education, employment history) will be captured.

9.1.2 ***Medical/Surgical/Family History***

Relevant medical and surgical history will be captured as well as relevant medical history of first-degree relatives. A list of current medications will also be documented.

9.1.3 ***Hearing and Vision Assessment***

Hearing and vision will be assessed at baseline. Vision and hearing ability will be assessed by questions on perceived visual and auditory ability and an inventory of aids used. Participants must have relatively sufficient vision (with corrective lenses or other aids) so that they can identify symbols, stimuli and text presented on a computer screen in front of them. Participants must also have sufficient hearing (corrected with hearing aids or other voice amplification devices) to be able to follow spoken instructions and information that is presented only verbally.

9.1.4 ***CAIDE Score***

The CAIDE Dementia Risk Score is a validated tool to predict late-life dementia risk (20 years later), based on midlife vascular risk factors [15]. Its components are age, education, sex, systolic blood pressure, body mass index, total cholesterol and physical activity. Participants will be asked about current vascular risk factors and history at mid-life (40-60 years old) to capture both a current and mid-life CAIDE Score. Since this remote study does not include an actual measure of blood pressure nor is there a blood draw for total cholesterol, the rating of these components will be based either on medical record review (if available) or on participant self-report (i.e. confirmation of physician diagnosis, medical treatment, other approaches to treatment). Physical activity is defined as engaging in a minimum of 20- 30 min of physical activity causing sweating and breathlessness, at least 2 times a week. BMI will be captured using the NIH BMI Metric Calculator (https://www.nhlbi.nih.gov/health/educational/lose_wt/BMI/bmi-m.htm).

9.1.5 ***Saliva Sample for Genomics Testing (Polygenic Hazard Score)***

A saliva sample collection kit (OG-500 kit, DNA Genotek, Kanata, Ontario) will be sent to each participant for extraction of DNA. Study staff at SRI will be responsible for mailing the kits to the

participant's home. The at-home kit will include detailed instructions on how to collect the sample and a study team member will provide guidance to the participant on how to properly collect and ship the sample during the Baseline video-call visit. A total of 2 mls of saliva will be collected by passive drool in 1 tube. Participants will be instructed not to eat, drink, smoke, or chew gum for 30 minutes prior to giving the sample. The samples will be collected, handled, stored and shipped according to established standard operating procedures. Instructions for collection, handling and shipping of saliva samples for DNA testing will also be provided in the Study Procedures Manual.

De-identified samples will be sent to the Clinical Genomics Centre in the Mount Sinai Hospital, [name], Canada and will be processed under the guidance of [name]. Samples will be stored for the duration of the study and until all planned analyses are complete, after which they will be properly destroyed according to established lab procedures.

A Polygenic Hazard Score (PHS) will be derived from a planned panel of single nucleotide polymorphisms that describes age of onset and ADD risk [16]. Both raw and processed data will be posted to the LORIS server.

9.1.6 ***Remote Neurological Exam***

A brief neurological examination will be conducted during screening by the site principal investigator or a designated medically qualified professional. The examination will be completed by a telemedicine visit using secure PIPEDA compliant video-conference technology (e.g. Zoom). The exam will be conducted following guidance from the American Academy of Neurology (AAN) and the Telemedicine and COVID-19 Implementation Guide (<https://www.aan.com/siteassets/home-page/tools-and-resources/practicing-neurologist-administrators/telemedicine-and-remote-care/20-telemedicine-and-covid19-v103.pdf>) and will include assessment of mental status, language, calculations, memory, cranial nerves, gate, motor, sensory, and cerebellar function.

9.2 ***Online Cognitive Testing***

Participants will be asked to complete cognitive testing remotely throughout the duration of the study. Participants will be provided with detailed instructions on each remote assessment at the baseline video-conference with a study team member. The following online cognitive assessments will be completed (see Schedule of Events ([Appendix 2](#)) for timing of assessments):

9.2.1 ***Cogniciti Brain Health Assessment***

The Cogniciti Brain Health Assessment (BHA) is a self-administered validated computerized cognitive assessment comprised of four tests (Spatial Working Memory, Stroop Interference, Face-Name Association, and Number-Letter Alternation). Total time to complete testing is approximately 20 minutes. Cogniciti technology allows for secure, remote, unsupervised assessment of participants using a web-based system and is compatible with any desktop and laptop device that has web browser capability and an internet connection. Participants will receive instructions from a study team member on how to complete testing at Baseline, Month 6, and Month 12 (see section [10.1.5](#) for full description of cognitive measures included in the Cogniciti BHA).

9.2.2 ***MyCogHealth App “Burst” Cognitive Testing***

MyCogHealth is an iOS/Android app for self-administered cognitive assessments and customizable surveys of health behaviors, risk factors, and patient-reported outcomes. The MyCogHealth app currently supports iPhones from version 6 and up (running iOS 11 and up). The app also supports Android 6 and up. The software is built on Health Insurance Portability & Accountability Act (HIPAA)-compliant scheduling and data management server-side software that permits individually tailored assessment protocols and scheduling. The platform is user-friendly and was developed for use with older adults. Based on available data pertaining to smartphone use and ownership in this age population, we anticipate that the majority of participants will have a personal smartphone that is compliant with this program. With assistance from a study team member, each participant will install the mobile application software on their personal mobile device. For individuals lacking a compliant smartphone, CTU will provide up to 150 participants with Android devices, including training. Participants will be oriented to the application software during the baseline remote video-conference, and will complete a training session on the mobile battery with the study team member present via video-conference to answer questions and trouble-shoot any issues that may arise. Ongoing technical support may also be provided to participants, over the duration of their participation in the 12-month BHSP, as needed through [name] CogTech Group at the University of Victoria. For the purposes of providing technical support, participant contact information (name, telephone number, email address) and study ID may be sent by encrypted email to study staff at the CogTech Group at the University of Victoria.

“Burst” cognitive testing using the MyCogHealth app will consist of five measurement “bursts” over approximately 12 months, at Baseline, Month 3, 6, 9 and 12. Each measurement burst will involve two mobile assessment sessions per day for seven consecutive days, with sessions that take approximately 5-10 minutes to complete. Each session includes 3 cognitive tests, Symbol Match, Dot Memory, and Trail-Making A and B, as well as several brief questions assessing state factors at the time of testing (e.g., mood, fatigue, subjective impression of cognitive ability). See section [10.1.6](#) for full description of cognitive measures.

9.3 ***Physical Activity and Sleep Monitoring***

Participants will be asked to participate in at-home physical activity and sleep monitoring throughout the duration of this study through the application of Actigraphy and EEG headband devices. Participant contact information (name, telephone number, email address, mailing address) and study ID will be sent by encrypted email to study staff at Sunnybrook Research Institute (SRI, University of Toronto, Ontario), a participating CTU site. Devices will be centrally distributed from SRI to participants and detailed instructions on application and use of devices will be provided to participants along with guidance from an SRI study team member via video-conference. For participants enrolled at French-speaking sites, a study team member from that site may assist SRI with participant communications.

Participants may also be invited in a sub-study, based at SRI ([Appendix 6](#)), which will add 24-hours of cardiopulmonary monitoring for sleep apnea and its physiological consequences using a pair of adhesive band-aid like sensors. The optional sub-study will be conducted under a separate study protocol with a separate consent form.

CTU will provide the Actigraphy devices, EEG headbands, and iPods to be used for the duration of this study, which should allow for all participants to participate in recordings at Baseline and Month 12. As described earlier, EEG recordings will be captured on the Muse app installed on the iPod.

9.3.1 Actigraphy

Physical activity and sleep monitoring using actigraphy (Axivity AX3) will be assessed at Baseline and Month 12. The Axivity is an accelerometer used to detect movement, vibrations, and orientation changes. The Axivity device will be mailed to participants. After study equipment and materials are shipped to and received by the participant, study staff will instruct the participant on the proper application and use of the Axivity over remote video-conference. The participant will be given an instruction card containing contact information of study staff should they have any questions. The participant will be shown how to place the device on their non-dominant wrist by study staff, and participants will be instructed to wear the devices continuously for 14 days, even when bathing or swimming. During the 14 days, participants will be asked to track their work and sleep hours in a diary. At the end of 14 days, participants will return the device to SRI using a pre-paid, pre-addressed package. This procedure will be repeated at the Month 12 remote visit.

9.3.2 *EEG Recording*

Overnight EEG recording will be assessed at Baseline and Month 12 using the MUSE S Headband (Interaxon Inc, Toronto, Ontario, Canada). The MUSE S Headband is a commercially-available consumer headband that has 5 sensors, 2 on the forehead, 2 behind the ears, plus 1 reference sensors, to detect and measure EEG signals. The EEG headband and iPod with Muse app installed will be mailed to participants. After study equipment and materials are shipped to and received by the participant, study staff will instruct the participant on the proper application and use of the Muse over remote video-conference. Participants will use the iPod with the Muse app to capture EEG sleep recordings. Study coordinators will use a pseudo email and password, which will be linked to a central study e-mail address (provided by the sleep team at SRI) to initially sign-up for the app prior to mailing the study iPod to participants. Recordings will be linked to the associated Muse headband device number only and will not include any PHI.

The participant will be given an instruction card containing contact information of study staff should they have any questions. On the night after the baseline visit, participants will wear the headband, start the recording using the provided iPod, and stop the recording the following morning. They will repeat this for an additional 2 nights (3 consecutive nights total), charging the devices in-between each recording according to the instructions provided, and then return the EEG headband, iPod, and the Axivity device described above, after 14 days of actigraphy. Participants will be provided with a pre-paid, pre-addressed package. Data is uploaded automatically from the iPod to a manufacturer-supported cloud server. Raw data will be downloaded from the cloud server, processed by the study team at SRI, and then will be uploaded to LORIS. This procedure will be repeated at the Month 12 visit.

9.4 Data Collection from other CCNA Studies

A subset of CTU: BHSP participants may be recruited from those participating in other CCNA studies such as COMPASS-ND and SYNERGIC-2. If participants consent to have their data

from other CCNA studies shared with CTU: BHSP, the following data will be accessible (via LORIS) for use within BHSP:

- Clinical Data
- Neuropsychological Testing
- Biospecimen

10.0 STUDY-SPECIFIC INSTRUMENTS

10.1 Cognitive Measures

10.1.1 *Clinical Dementia Rating (CDR)*

The CDR is a validated 5-point composite scale used in longitudinal AD research to characterize cognitive and global function performance applicable to AD and related dementias [21]. Information is obtained through a semi-structured interview of the patient and a reliable informant or collateral source (e.g. family member). The three cognitive domains include memory, orientation, and judgment/problem solving and the three functional domains include community affairs, home and hobbies and personal care. The five possible scores for each domain [0, 0.5, 1, 2, and 3] represent a range of impairment (e.g. score of 0 represents no impairment and a score of 3 represents severe impairment). If an informant is not available, the CDR score will be decided by site-level research team consensus based on all other available information and utilizing best clinical judgement.

10.1.2 *Logical Memory I and II*

Logical Memory I and II (Story A) from the Wechsler memory scale [22] will be completed during remote screening by tele/video-conference. The participant will be instructed to listen to a story and repeat it back after it has been read. They will then be asked to recall the story approximately 30 minutes later.

10.1.3 *Montreal Cognitive Assessment (MoCA)*

The MoCA is a 10-minute test that provides a global assessment of cognition, covering domains of memory, language, attention, visuospatial, and executive functioning [23]. An audiovisual version of the full MoCA has been validated for remote administration by video-conference[24]. Instructions for administration of full MoCA by video-conference can be found at <https://www.mocatest.org/remote-moca-testing/>.

10.1.4 *Neuropsychological Test Battery (NTB)*

The NTB will be administered remotely at baseline and Month 12 by video-conference. The sessions will be audio recorded to facilitate rater scoring and for quality control. Full details on rater training and the administration for remote testing will be provided in the Study Procedures Manual.

Participants will receive all necessary testing materials by mail ahead of the testing session. The battery requires approximately 1.0-1.5 hours to administer.

Tests that have been administered clinically in the past 12 months will not be repeated (unless there is a discrepancy between test versions). Consent forms for each site will include a statement asking participants to allow for their clinical results from tests overlapping with the CTU battery to be entered into the CTU case report form. If a patient was assessed using a different version of the same test used in the CTU neuropsychological battery, the test will be repeated using the version consistent with the study.

Domain	Test	Description	Time (Mins)
Memory & Orientation	Craft Story 21 Immediate and Delayed Recall	Story learning and Recall	10-15
	ADAS-Cog Immediate & Delayed Word Recall	Word List Learning and Recall	10-15
	ADAS-Cog Orientation	Orientation	2-3
	Brief Visuospatial Memory Test - Revised	Figure learning and Recall	10-15
Attention, Processing Speed	Digit Symbol Modalities Test- Oral Version	Attention and Processing speed	5
	Oral Trail Making Test (Part A)	Visual and Motor Processing Speed	2-3
	DKEFS Color-Word Interference Test- Color Naming & Word Reading	Attention and Processing Speed	5
Executive Function	DKEFS Verbal Fluency	Phonemic (letter) fluency, Semantic (category) fluency, Category Switching	2
	Oral Trail Making Test (Part B)	Switching attention	3-5
	DKEFS Color-Word Interference Test- Inhibition	Inhibition	5-10
Visuoperceptual & Construction	Brief Visuospatial Memory Test- Revised Copy	Visuoconstruction	3
Speech & Language	Boston Naming Test-15 Item	Confrontational Naming	5-10

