8.1.3.1 Video-Conference Baseline Procedures

Participants who are enrolled in the study will complete the following baseline procedures remotely via video-conference with a member of the study team. (Estimated Time to Complete: 2.5-3.0 hours)

Participants may complete screening and baseline assessments at the same remote visit as long as the participant (and study partner if applicable) have provided consent prior to initiating any study-specific procedure and the site Study Investigator has confirmed study eligibility. Baseline procedures may also be completed over multiple days as long as all procedures are completed within 14 days of the first baseline video-call visit.

- Neuropsychological Test Battery (adapted for remote administration; see section [10.1.4](#) for test descriptions and information on remote administration; estimated time to complete is 1.0-1.5 hours)
 - Craft Story 21 Immediate and Delayed Recall
 - ADAS-Cog word recall, delayed recall, orientation
 - Brief Visuospatial Memory Test-Revised (BVMT-R)
 - Delis-Kaplan Executive Function System (DKEFS) Verbal Fluency
 - Oral Trail Making Test A and B
 - DKEFS Color-Word Interference Test
 - Oral Symbol Digit Substitution Test
 - Boston Naming Test (BNT) 15-Item
 - “Burst” Cognitive Testing (training session)
- Self-report height and weight
- Body Mass Index (BMI) calculation (based on self-report current height and weight)
- Saliva sample collection for genomics testing (Polygenic Hazard Score; with at-home collection kit)
- Instructions on how to complete “Burst” Cognitive Testing and completion of training testing session

- Instructions on how to complete the Cogniciti Brain Health Assessment
- Instructions and application of wearables for actigraphy and EEG recordings (see section [9.3](#))
- Instructions on how to register and participate in BHPro (see section [8.3](#))

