8.4.4 Cognition

8.4.4.1 Change in **global cognition** will be assessed using a composite outcome score computed from the following measures from Neuropsychological Test Battery:

- Craft Story – Immediate Recall – Total Story Units Recalled - Verbatim
- Craft Story – Delayed Recall – Total Story Units Recalled - Verbatim
- ADAS-COG Word Recall – Total Immediate Recall (trial 1 + trial 2 + trial 3)
- ADAS-COG Word Recall – Delay (total correct)
- Brief Visuospatial Memory Test-Revised (BVMT-R)- Total Recall (trial 1 + trial 2 + trial 3)
- BVMT-R Delayed Recall
- Oral Symbol Digit Modalities Test – Total Raw Score
- Oral Trail Making Test (Part A) – Time To Completion
- Oral Trail Making Test (Part B-A)
- DKEFS Category Fluency – Total Correct (animals only)
- DKEFS Color-Word Interference Test (CWIT) – Condition 2 Word Reading – Time to Complete

- DKEFS CWIT – (Condition 3 Inhibition-Condition 2 Word Reading)

Z-scores for each participant on each measure will be calculated using the overall mean and SD of all participants at baseline as reference. Scores from each individual test will be converted to z-scores that typically range from -3 to 3, with higher scores reflecting better performance, and averaged to form a composite. For purposes of this analysis, the z scores for the timed tasks (Oral Trail Making Test (Part A and Part B) and Color-Word Interference Test (Word Reading and Inhibition)) are reverse coded. If more than 25% of the component measures are missing, the global cognitive composite score will be missing.

An MMRM will be used to evaluate change in the global cognitive outcome from baseline to Month 12, adjusted for baseline characteristics including age, sex, race, cognitive status and education. The MMRM will be fit to the ITT sample (that is, the same multiply imputed dataset described in section 8.1), to the mITT sample, and to the 'completers' sample. Inference on the change will be conducted through least-square means estimates.

Additional exploratory analysis will be conducted by analyzing the data obtained by first calculating the domain-specific outcomes (see section 8.4.4.2 below), and then aggregating the domain-specific outcomes to calculate the global cognitive outcome score. Methods similar to the above will be used for the analysis.

8.4.4.2 Change in the subdomains of memory, processing speed, and executive functions will be assessed using domain-specific composites.

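### Clinical neuropsychological scores up to 12 months old may replace study tests, with no visit, date-window or mode limit, so the exploratory cognition change scores can mix intervals and administration modes

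*Protocol*

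**What the plan says.** Protocol 10.1.4 opens with the general rule: "The NTB will be administered remotely at baseline and Month 12 by video-conference". The Schedule of Events (Appendix 2) marks the NTB tests at Baseline and Month 12 only, each within 2 weeks either way, and its footnote 6 calls for a trained rater on video. Section 8.1.3.1 lets baseline testing run over several days as long as "all procedures are completed within 14 days of the first baseline video-call visit".

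The same section 10.1.4 then makes an exception: "Tests that have been administered clinically in the past 12 months will not be repeated". Consent forms ask participants to allow "clinical results from tests overlapping with the CTU battery to be entered into the CTU case report form". The one stated ground for repeating a test is that a different version was used, in which case "the test will be repeated using the version consistent with the study". Date and mode are not mentioned.

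SAP 8.4.4.1 and 8.4.4.2 analyse change from baseline to Month 12 in the global and domain composites. Both sections standardise in the same way: "Z-scores for each participant on each measure will be calculated using the overall mean and SD of all participants at baseline as reference". Neither mentions substituted scores.

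**The concern.** A score obtained outside the study can enter the dataset labelled as Baseline or Month 12 although it was taken at another time, perhaps in person, and by a rater the study did not train. Substitution works test by test, so a single composite can average components from different dates and modes.

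The design gives little protection. This is a one-group pre/post study, so a shift in timing or mode goes straight into the estimated change. The model in SAP 8.1 uses nominal visit as a factor and has no term for actual test date or mode. A substituted score counts as observed, so the multiple imputation leaves it as it is. What is at stake is the interpretation of the exploratory NTB composites, and of the planned concordance analyses that compare the NTB with the online cognitive tests.

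**Working it through.** **The plan's own figure.** No figure in the plan bears directly on this point. The nearest is Table 1 of Protocol 13.1, which concerns the primary outcome. Its eight entries reproduce from the Appendix 4 formula after rounding up. For ES 0.2 and r 0.3, (1.96 + 0.84)² × 2(1 − 0.3) / 0.2² + 2 = 276.4, so 277. They do not depend on the NTB.

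**Inputs from the documents.** Look-back 12 months (taken as 365 days); Month 12 window ±14 days; programme 45 weeks = 315 days (Protocol 8.3); 12 measures in the global composite and 6 in memory, of which BVMT-R supplies 2 in each (SAP 8.4.4.1 and 8.4.4.2).

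**Inputs that are assumptions.** The share of participants with a substituted score (p), the spread of test dates, how change accrues, and the size of any mode shift.

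**Interval between the two scores**

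| Case | Days |
|---|---|
| As scheduled | 365 − 14 = 351 to 365 + 14 = 379 |
| Baseline score substituted | up to 365 + 379 = 744 (about 24 months) |
| Month 12 score substituted, if the rule applies there | down to 0 |

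In the last case, a Month 12 visit held 14 days early has a look-back reaching 351 − 365 = −14 days. One clinical result could then qualify at both visits and give a change of exactly zero. These are the outer limits, not typical values.

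**Dilution if Month 12 scores are substituted.** With test dates spread evenly over the year, a share 315/365 = 86% would fall before the programme ends. With change accruing linearly over the year, a substituted score carries on average s = 0.5 of the full change. If k of K measures are replaced and all measures change equally, dilution = p × (1 − s) × k/K.

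| Measures replaced | p = 5% | p = 20% | p = 30% |
|---|---|---|---|
| BVMT-R in global (2/12) | 0.4% | 1.7% | 2.5% |
| BVMT-R in memory (2/6) | 0.8% | 3.3% | 5.0% |
| All measures | 2.5% | 10% | 15% |

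If change instead accrues over 315 days and then holds, s = (315/2 + 50)/365 = 0.568. At p = 20% the three figures become 1.4%, 2.9% and 8.6%.

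**If only baseline scores are substituted.** An older score still precedes the intervention, so exposure is not diluted. The longer interval and a possible mode difference remain.

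**Mode shift.** With an assumed shift of 0.2 to 0.5 SD of the composite, at one visit only, in 5% to 30% of participants with every measure replaced, bias in mean change is 0.05 × 0.2 = 0.01 SD to 0.30 × 0.5 = 0.15 SD. With 2 of 12 measures shifted by the same amounts it is about one sixth of that, 0.002 to 0.025. For scale, the standard error of mean change is √(2(1 − r)/n). That is 0.064 SD for n = 245, r = 0.5 and 0.038 SD for n = 280, r = 0.8 (both r values assumed).

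**Standardisation.** Substituted baseline scores enter the reference mean and SD. The same reference is used at both visits, so the mean cancels from a change score. The effect on change comes through the SD, which sets the scale of each measure.

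**The case against.** The case on the other side is substantial, and it rules out several stronger readings.

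- **That Month 12 scores will be substituted.** The rule names no visit, but Protocol 8.1.8 lists the battery among the procedures participants undergo at Month 12. The sponsor may well have meant baseline only. The Month 12 route is an inference from unrestricted wording, and every dilution figure depends on it.
- **That the section contradicts itself.** The no-repeat rule is better read as an exception to the general rule above it. The fault is that the exception has no date or mode limits.
- **That substitution is common.** Protocol 9.4 says "A subset of CTU: BHSP participants may be recruited from those participating in other CCNA studies such as COMPASS-ND and SYNERGIC-2", but it concerns sharing data from research studies and does not say those scores replace NTB testing; the exception covers clinical tests. Section 6.0 mentions clinic registries only as a possible source beside a national campaign. The frequency is unknown.
- **That global change is diluted by 10%.** That needs an unsourced 20% and replacement of all 12 measures. The rule works one test at a time.
- **That any in-person score passes.** Some NTB tests are oral versions, and section 10.1.4.8 distinguishes oral from written Trail Making, so a written test would be repeated. The protocol also describes the battery as adapted for remote use. However, version is not defined by mode, so a same-version in-person score can still qualify.

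The Study Procedures Manual may require test date and mode to be recorded; that cannot be determined from these documents. Repeating a recently taken test also brings a short-interval practice effect.

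What stands is narrower. Even read as baseline only, the text admits baseline scores up to a year old and possibly in another mode, and the SAP neither identifies nor tests their influence.

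**Conclusion.** The concern holds for the exploratory NTB composites and the analyses built on them. Following the plan as written can place clinical scores up to 12 months old, in an unspecified mode, at the nominal baseline. Because no visit is named, it can also place scores from earlier in the programme at Month 12. The change estimates can then mix test intervals and modes, with nothing in the design or model to separate them.

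The size is uncertain. At an assumed 20% substitution at Month 12, spread evenly, dilution of global change runs from about 1.7% (BVMT-R only) to 10% (all measures). It is zero if the rule applies only at baseline, where interval and mode differences remain. Mode bias cannot be sized from the documents.

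A reader might infer that the trial's main result is at risk. It is not: the ADKS and GSE are completed online within BHPro (Protocol 10.3) and are not covered by the rule, and the sample size rests on the primary outcome.

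**What to change.** **Protocol 10.1.4.** For NTB outcome scores, remove the substitution. Alternatively, accept an outside score only if it is the same version, was given by video, and falls inside that visit's own window. State the visits to which any remaining exception applies, and require the test date and mode to be recorded.

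**Data already collected.** Flag each substituted score with its date and mode. In the imputed ITT analysis, treat out-of-window scores as missing. Add to SAP 8.4.4 a sensitivity analysis that excludes all substituted scores, and report how many there were by test and visit.

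**Cost.** The protocol edit is small, and the session of 1.0 to 1.5 hours is already scheduled. Some participants will repeat a recently taken test, with the practice effect that brings. Setting scores to missing can also remove composites from the mITT and Completers analyses, which use observed data. Losing the two BVMT-R measures leaves 10 of 12 (17% missing, under the 25% limit) and 4 of 6 for memory (above the 50% minimum), so both composites survive if nothing else is missing. Losing four or more of the 12 makes the global composite missing. If substitution was rare, the extra analysis costs little and shows it.
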